#### **7.1.5. Missing data**

Missing data will be imputed as described above in [Section 7.1.2](#).

#### **7.2. Sample size**

The true population mean %TBL in the control group is assumed to be 3.3% based on the Orbera and ReShape PMA studies. The standard deviation of %TBL is assumed to be approximately 6.6%, based on 6-month data from the Orbera PMA study. Based on these two assumptions, and a true population mean %TBL in the Spatz3 group of 10.34%, a total sample size of 240 subjects randomized 2:1 (160 in the Spatz3 group and 80 in the control group) will provide 80% power to demonstrate super-superiority of 4.5% TBL over the control at a one-sided significance of 2.5%. To account for a potential dropout rate of 15%, the final total sample size is 282 subjects randomized 2:1 (188 in the Spatz3 group and 94 in the control group).

#### **7.3. Safety**

All adverse events and all serious adverse events will be summarized by treatment group as the first occurrence for each subject. These adverse events will also be presented by causality. In addition, the number and percent of subjects with balloon deflation will be summarized.

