# Spatz 3 US Pivotal Trial Protocol

Protocol Version	V1.4e (January 11, 2017)
Sponsor	Spatz FGIA [name] Contact Person: [name] CEO, Spatz FGIA, Inc [contact]
Trial Title	A randomized, controlled, multicenter study comparing the Spatz3 Adjustable Balloon System plus diet and exercise to diet and exercise alone.
Device Name	Spatz3 Adjustable Balloon System® (Spatz3)
Clinical Phase	Pivotal
Trial Design	Multicenter open-label randomized controlled trial
Trial Participants	Adults with a BMI $\geq$ 30 and $<$ 40 who have failed to achieve and maintain weight-loss with a weight control program
Control group	Supervised diet and exercise
Planned sample size	282 subjects randomized 2:1 to device/control
Follow-up duration	8 months for control and 14 months for treatment
Planned trial period	30 months
Primary endpoints	Percent change in total body weight (%TBL) at 32 weeks AND Clinical response, where a responder is defined as a subject with at least a 5% loss in total body weight at 32 weeks
Secondary endpoints	Maintenance of 40% of the weight loss with the balloon six months after the balloon is removed Clinical response, where a responder is defined as a subject with at least a 25% loss in excess body weight at 32 weeks

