#### **3.3. Design**

The purpose of this study is to evaluate the safety and effectiveness of the Spatz3 in subjects with a BMI  $\geq 30$  and  $< 40$  who have failed to achieve and maintain weight-loss with a weight control program.

Subjects will be studied in a randomized, controlled, multi-center study. The control group will receive dietary/exercise counseling for 32 weeks. The treatment group will receive dietary/exercise counseling plus the Spatz3 balloon for 32 weeks.

The study will run 32 weeks for the control group and 32 weeks followed by a 24-week follow up period for the treatment group.

282 eligible subjects will be randomized to treatment (188 subjects) or control (94 subjects) arms. All treatment group subjects will undergo endoscopy and those without endoscopic contraindications will be implanted with the Spatz3 balloon for 32 weeks. All subjects will follow a 1000-1200 kcal/day-deficit diet during their participation in the study.

At 18 weeks  $\pm$  4 weeks, treatment arm subjects will be evaluated, and those that meet the criteria described below in section 4.3.3.2.4 will undergo an adjustment procedure wherein the balloon volume will be increased to achieve extra weight loss. The balloon adjustment procedure is done with an endoscopy procedure under the same sedation as the implantation procedure. At the end of the 32-week treatment period the control subjects will be dismissed and the treatment group will be explanted and will have a 24-week follow up.

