#### 4.3.4. Follow-Up Schedule

Follow-up visits for treatment and control patients will occur according to the following schedule: Visits at 1 week, 2 weeks, and 4 weeks ( $\pm$  3 days), and thereafter every 4 weeks ( $\pm$  2 weeks) until primary endpoint assessment at 32 weeks. In addition, 1-2 weeks after the adjustment procedure the subject will have a follow up appointment with the PI/NP.

Each follow-up visit will include:

1. Clinical assessment by PI or nurse practitioner or physician’s assistant for both the treatment group and control group (*Appendix E6: CRF6\_Control Group PI Follow Up* or *Appendix E7: CRF7\_Treatment Group PI Follow Up*)
2. Satiety and Dietary Assessment for both the treatment group and control group - limited to 30-45 minutes per session (*Appendix E8: CRF8\_Control Group Dietician Follow Up* or *Appendix E9: CRF9\_Treatment Group Dietician Follow Up*)
3. Record adverse events, device complications, concomitant medication (*Appendix E6: CRF6\_Control Group PI Follow Up* or *Appendix E7: CRF7\_Treatment Group PI Follow Up*)
4. Weight to be done by staff (patient may not speak with weighing personnel and may not disclose if they are control or treatment arm)

Control patients will exit the study at Week 32. Treatment patients will have the device explanted and will be followed for an additional 24 weeks according to the following schedule: Visits at Week 36 ( $\pm$  3 days) and thereafter every 4 weeks ( $\pm$  2 weeks) until 56 weeks. Treatment patients who undergo balloon extraction prior to 32 weeks will be followed from the time of balloon extraction an additional 24 weeks according to the following schedule: Visits at 4 Weeks post extraction ( $\pm$  3 days) and thereafter every 4 weeks ( $\pm$  2 weeks) until 24 weeks after the extraction.

These follow-up visits for the treatment group only, will include:

1. Clinical Assessment - only at the visit 4 weeks post extraction(*Appendix E7: CRF7\_Treatment Group PI Follow Up*)
2. Satiety and Dietary Assessment (*Appendix E9: CRF9\_Treatment Group Dietician Follow Up*)

A summary of required visits and procedures for subjects who do not require an unscheduled endoscopy is shown in the following table and provided in *Appendix B: Study Visits and Master Schedule*:

Assessment / Procedure	Screening Assessments	7 Days Prior to implant	Implantation	Adjustment	Explantation	Follow-Up Assessment weeks 1-32	WEEKS 36 - 56
Informed Consent	X						
Date of birth/gender	X						

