Body Weight	X	X	X	X	X	X	X
Body Height	X						
BMI	X	X	X			X* (week 32)	X * (week 56, or 24 weeks after extraction)
Ideal weight/ Excess Weight	X				X	X* (week 32)	X * (week 56, or 24 weeks

Assessment / Procedure	Screening Assessments	7 Days Prior to implant	Implantation	Adjustment	Explantation	Follow-Up Assessment weeks 1-32	WEEKS 36 - 56
							after extraction)
Medical History	X						
Physical Exam 	X			X	X		Week 36, or 4 weeks after extraction
Blood Pressure	x		X	X	X	X	Week 36, or 4 weeks after extraction
CBC  Coag  (Coag @ screen only)	X						Week 36, or 4 weeks after extraction
H. Pylori Serology	X						
Chemistry Panel 	X						X Week 36, or 4 weeks after extraction
HgbA1C2 IF DIABETIC	X						X Week 36, or 4 weeks after extraction
EKG*(Females and Males >40 y/o	X						
Psychological Evaluation	X						
Inclusion and Exclusion Criteria	X						
Develop/Review Dietary Plan	X						
Satiety and Dietary Assessment						X	X (or 24 weeks after extraction)
Investigator or Nurse follow up				X	X	X	X (or 24 weeks after extraction)
Medications List	X	X				X	X Week 36, or 4 weeks

 Investigator or co-investigator must perform physical exam.

 See section 4.3.1 for required tests

Assessment / Procedure	Screening Assessments	7 Days Prior to implant	Implantation	Adjustment	Explantation	Follow-Up Assessment weeks 1-32	WEEKS 36 - 56
							after extraction
Urine Pregnancy Test women of child bearing potential*	X	X					
Adverse Events/Device Complications			X	X	X	X	X
Verify Birth Control for Females	X						

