**6.2.3. Procedures for recording adverse events**

It is the responsibility of the local investigator to ensure that all adverse events (AEs, ADEs, and device deficiencies) occurring during the course of the study are recorded. This may include but not be limited to:

- A description of the event
- The dates of the onset and resolution
- Action taken
- Outcome
- Initial assessment of relatedness to the device (final adjudication will be made by the DMC)
  - a. Whether the AE is serious or not
  - b. Whether the AE arises from device deficiency
  - c. Whether the AE arises from user error

Adverse events that occur during the course of the study should be treated by established standards of care that will protect the life and health of the study subjects

It is the responsibility of the local investigator to collect all directly observed adverse events and all adverse events spontaneously reported by the subject. In addition, each subject should be questioned about adverse events at each visit. Adverse events should be recorded on provided serious adverse event data collection forms.

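### Section 7.3 sets no time window for the by-arm AE and SAE summaries, so 32 weeks of control follow-up are set against up to 56 weeks in the device arm

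*Combined protocol and SAP*

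**What the plan says.** Section 7.3 governs the final safety tables: "All adverse events and all serious adverse events will be summarized by treatment group as the first occurrence for each subject". It adds a presentation by causality and a count of balloon deflations. It gives no cut-off week, no on-device or post-extraction split, and no adjustment for length of follow-up. Section 3.2.2, the safety endpoint, gives none either.

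The two arms are observed for different lengths by design:

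- The synopsis gives follow-up as "8 months for control and 14 months for treatment".
- Section 3.3: "The study will run 32 weeks for the control group and 32 weeks followed by a 24-week follow up period for the treatment group".
- Section 4.3.4: "Control patients will exit the study at Week 32".
- Section 4.3.4, on early removal: "Treatment patients who undergo balloon extraction prior to 32 weeks will be followed from the time of balloon extraction an additional 24 weeks".

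AE data are collected in the extra weeks. In the Section 4.3.4 visit table, the row "Adverse Events/Device Complications" is marked under Weeks 36-56, and Section 6.2.3 says that "each subject should be questioned about adverse events at each visit". However, the numbered list of what post-extraction visits include (Section 4.3.4) does not repeat AE recording, and it limits the clinical assessment to the visit 4 weeks after extraction.

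**The concern.** In a by-arm AE table, the control column shows how often events occur without the device. That works only if both columns cover the same period. A programmer following Section 7.3 would count every recorded event, so the device column would include post-extraction events for which no control was under observation. An intercurrent illness unrelated to the balloon would then look more frequent on the device simply because it was counted for longer, and the incidence table alone would not let a reader separate this from a device effect. Safety is part of the study's stated purpose in Section 3.3, so the table should be readable at face value.

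**Working it through.** The plan states no numerical figure for the safety summaries, so the check starts from its follow-up figures.

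**1. Planned follow-up (synopsis; Sections 3.3 and 4.3.4).** Control 32 weeks; device 32 + 24 = 56 weeks. Ratio 56/32 = 1.75. The synopsis months give the same: 14/8 = 1.75.

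**2. Planned maximum person-time (188 device, 94 control; Section 3.3).** Device 188 × 56 = 10,528 person-weeks; control 94 × 32 = 3,008. Ratio 3.5, against 2:1 allocation. With both arms cut at Week 32, device is 188 × 32 = 6,016 and the ratio returns to 2.0.

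**3. Early extraction.** A subject explanted at week w has w + 24 weeks of planned follow-up: 28 for w = 4, 32 for w = 8, 36 for w = 12. Below Week 8 the total is shorter than in a control. Section 2.2 cites 4.2% to 6.7% early removals for earlier balloons. Assuming removal at Week 12, mean device follow-up is (1 − e) × 56 + e × 36:

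- e = 0.042: 55.2 weeks, ratio 1.72
- e = 0.067: 54.7 weeks, ratio 1.71

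Early removal at these rates hardly changes the arm average.

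**4. Effect on a background event with the same hazard in both arms.** The 32-week incidences p are assumptions.

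- Constant hazard: 1 − (1 − p)^(56/32).
- Front-loaded: 80% of the 32-week cumulative hazard in Weeks 0-4, the other 20% spread evenly over Weeks 4-32 and continuing at that rate to Week 56. The multiplier is 1 + 0.2 × 24/28 = 1.171, giving 1 − (1 − p)^1.171.

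| Control, 32 weeks | Device, 56 weeks, front-loaded | Device, 56 weeks, constant |
|---|---|---|
| 2% | 2.3% | 3.5% |
| 5% | 5.8% | 8.6% |
| 10% | 11.6% | 16.8% |
| 20% | 23.0% | 32.3% |
| 30% | 34.2% | 46.4% |

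Under a constant hazard the apparent relative risk is about 1.5 to 1.7 from follow-up length alone. With the early removals of step 3, 16.8% becomes 16.6% to 16.5%. For one subject at 10% risk, explant at Week 12 gives 1 − 0.9^(36/32) = 11.2%. Explant at Week 4 gives 1 − 0.9^(28/32) = 8.8%, so the direction reverses.

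**5. Does another planned analysis remove the difference?** No. The causality presentation (7.3) and the AE analyses by number of adjustments and balloon volume (7.1.4) set no period. The Kaplan-Meier calculation (6.1 and 6.3.2) covers only gastric ulcer in implanted subjects, for DMC monitoring.

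**The case against.** The best defence is that little harm follows. The safety endpoint in Section 3.2.2 concerns device-related events, which describes the device arm and is not a contrast between arms. No safety test is planned. Section 7.3 presents events by causality, and relatedness is finally adjudicated by the DMC (6.2.3), which helps a reader set background events aside. The distortion generally counts against the device, so it does not hide harm. All of this stands and limits the importance of the point. It does not remove it: the causality presentation covers the same unequal periods, and attribution in an open-label trial is an imperfect substitute for a control column over equal time.

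The size is also open to challenge. The 16.8% needs a constant hazard and equal ascertainment throughout. Because the post-extraction visit list does not repeat AE recording, ascertainment may be thinner there, although the visit table and Section 6.2.3 require it. The main device symptoms are early: Section 2.2 reports nausea and vomiting in 85% of patients within 3 days for two earlier balloons. A subject already counted for such an event cannot be counted again, so the longer window adds little. Hence 16.8% is an upper figure within a range, not an expected value.

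A reader might also infer that Section 7.3 fails to deliver the frequency and severity promised in Section 3.2.2. The documents do not support that as a defect: the commitment is made in 3.2.2 and severity grades are defined in 6.2.1. Only the table layout is unwritten.

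**Conclusion.** The point holds as a gap in the analysis rule that should be closed. As written, the by-arm AE and SAE incidences cover 32 weeks against up to 56 weeks (planned ratio 1.75). For a background event assumed at 10% over 32 weeks, the device arm would read about 11.6% to at most 16.8% with no device effect. These figures assume equal hazards, equal ascertainment and the two hazard shapes shown.

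Two stronger readings are not supported. One is that the safety or effectiveness conclusions are invalid: the tables are descriptive, no between-arm safety test is planned, and power, type I error and the co-primary endpoints are untouched. The other is that every device incidence is inflated by 1.75: events near implantation barely move, and subjects explanted before Week 8 may be followed for less time than controls.

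**What to change.** Amend Section 7.3 as follows.

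1. Make the between-arm AE and SAE tables count first occurrences with onset from the day assignment is disclosed (Section 4.3.2: implantation day, or the dietician appointment for controls) through a fixed common study day, nominal Week 32 (32 × 7 = Day 224), or the subject's exit if earlier. Apply this in both arms. A fixed day is needed because visits carry a window of ±2 weeks.
2. Report device-arm events with onset after that day in a separate device-only table. Put extraction-procedure events on a labelled line that says in which table they are already counted.
3. Keep a whole-study, device-only first-occurrence table, so that cumulative device-arm incidence is not lost, and keep the presentation by causality.

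State the limits beside the tables. The cut equalizes calendar time but not contact: before Week 32 the device arm also has AE collection at implantation, adjustment and explantation, and "1-2 weeks after the adjustment procedure the subject will have a follow up appointment with the PI/NP". Subjects explanted before Week 8 may contribute less than 32 weeks.

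The cost is SAP wording and one or two extra tables. Onset dates are already recorded under Section 6.2.3, so no new data are needed.

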##### **3.2.2. Safety**

The incidence, frequency, and severity of adverse events related to treatment with the device will be reported.

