### *4. 18- week adjustment*

At 18 weeks ± 4 weeks, all treatment arm subjects whose balloon has not been removed will be evaluated to determine if an upward adjustment is clinically appropriate. The following algorithm will be followed:

1. Subjects who have reached goal weight (calculated by BMI of 25) **and** are without any symptoms of gastroesophageal reflux or symptoms suggestive of gastritis or gastric ulcer, will not receive a balloon volume adjustment, and endoscopy at 18± 4 weeks will not be performed.
2. Subjects who underwent a prior unscheduled endoscopy with findings of a gastric ulcer will not receive an adjustment at 18± 4 weeks and no additional endoscopy beyond that described in section 2 above will be performed.
3. For all other subjects, endoscopy will be performed, and adjustments/treatment decisions will reflect the following algorithm:
  - a. For subjects with gastric ulceration found at endoscopy, **no upward adjustment** and PI will decide if balloon requires extraction based on endoscopic findings as described below.

Subjects who present with an endoscopically confirmed gastric ulcer will be treated as follows:

- **Ulcers whose smallest dimension (S) is  $\geq 2$ cm, or if there are any stigmata of increased risk of bleeding, such as visible vessels or clots**

The balloon should be extracted. Biopsy for H.pylori will be performed and treatment prescribed if positive.

These subjects should be treated with the following regimen: with sucralfate 1,000 mg PO Qid, and PPI medication twice daily for 3 months, followed by endoscopic evaluation after 3 months to confirm healing.

- **Ulcers whose smallest dimension (S) is  $\geq 1$  cm and  $< 2$  cm**

The balloon volume should be decreased by 150 ml (or 100 ml if starting volume is 400 ml) and subjects should be treated with the following regimen: sucralfate 1,000 mg PO Qid and increasing PPI medication to twice daily for 2 months. A biopsy for H.pylori will be taken and treatment prescribed if positive.

Endoscopic follow up will be performed at 8 weeks and if not healed at 8 weeks, an additional endoscopy at 16 weeks to confirm healing.

- At the 8-week follow-up, if signs of healing defined by a 25% reduction in either length or width are not observed, then the balloon should be extracted.

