#### **4.3.3.2.6. Extraction**

The extraction procedure requires the patient to be on the following dietary restrictions:

- 72 hours prior to the procedure: Soft food only, no meat or vegetables in any form.
- 48 hours prior to the procedure: Full liquids only.
- 24 hours prior to the procedure: Clear liquids only.
- 12 hours prior to the procedure: No food or liquids by mouth.

The extraction procedure is performed under conscious sedation by the anesthetist similar to the implantation procedure. The endoscope is introduced in the usual manner. The capped valve is identified and the suture loop is grasped with a standard rat tooth grasping forceps. The scope and cap are pulled out of the mouth, wherein the cap is twisted off. A large polypectomy snare is inserted into the biopsy channel of the scope and the snare is opened and placed on the valve. Then the extension tube (provided) is connected to the valve. The scope (with snare closed on the valve) and the extension tube are lowered down the throat into the esophagus. The balloon deflation commences by utilizing the 3-way stopcock on the proximal end of the extension tube. Following completion of the deflation, the scope is pushed down to the gastro-esophageal junction to confirm complete deflation of the balloon. The snare is opened as the extension tube is pulled until the valve exits the mouth- this will bring the distal white catheter and deflated balloon edge into the open snare. The snare is closed. The scope (with snare secured around balloon/white catheter) and the stretched inflation tube are pulled out together with the balloon in tow. The scope is then reinserted to inspect for any mucosal damage.

Following the extraction procedure, all treatment subjects will be followed for an additional 24 weeks.

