##### **Adverse Event**

Any untoward medical occurrence, unintended disease or injury, or untoward clinical signs (including abnormal laboratory findings) whether or not related to the study intervention.

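### In the Section 7.3 tables the control column is no background rate for mucosal and scheduled-laboratory adverse events, because the protocol looks for them only in the Spatz3 arm

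*Combined protocol and SAP*

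**What the plan says.** The safety endpoint in Section 3.2.2 is descriptive: "The incidence, frequency, and severity of adverse events related to treatment with the device will be reported". Section 7.3 is wider. It covers every event, related or not: "All adverse events and all serious adverse events will be summarized by treatment group as the first occurrence for each subject". It adds a presentation by causality and a count of balloon deflations. It sets no common time window and does not separate events by how they were found.

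The adverse event definition in Section 6.2.1 starts from untoward occurrences, disease and injury and continues "or untoward clinical signs (including abnormal laboratory findings) whether or not related to the study intervention".

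Looking for such events is arranged differently in the two arms:

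- Implantation (Section 3.3): "All treatment group subjects will undergo endoscopy and those without endoscopic contraindications will be implanted with the Spatz3 balloon for 32 weeks".
- 18 ± 4 weeks (Section 4.3.3.2.5, item 4). Two groups are exempt: subjects at goal weight without relevant symptoms, and subjects with an ulcer at an earlier unscheduled endoscopy. Then: "For all other subjects, endoscopy will be performed, and adjustments/treatment decisions will reflect the following algorithm".
- Four weeks after adjustment, if the final volume is above 900 ml (Section 4.3.3.2.5, item 6).
- Extraction (Section 4.3.3.2.6): "The scope is then reinserted to inspect for any mucosal damage".
- Unscheduled endoscopy and ulcer follow-up endoscopies, which are provided for only under the Treatment Group heading.

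Section 4.3.3.1 gives controls diet and exercise counselling and lists no endoscopy. In the Section 4.3.4 visit table, blood count and chemistry are marked at screening and then only at Week 36 or four weeks after extraction. The Weeks 1–32 column has no laboratory entry. For controls, Section 4.3.4 says: "Control patients will exit the study at Week 32".

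**The concern.** A table with a Spatz3 column and a control column invites the reader to subtract one from the other. That is reasonable when both arms were observed in the same way. For lesions that cause no symptoms, and for abnormalities seen only on a scheduled panel, they were not. A Spatz3 subject with a silent erosion is likely to be recorded. A control with the same erosion will not be, unless care outside the protocol happens to reveal it.

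Three sets of rows are exposed: the gastrointestinal mucosal rows, any laboratory rows, and the overall rate of subjects with at least one event. The causality presentation is exposed too, since an unrelated lesion in Spatz3 has no control counterpart. What is at stake is how the safety profile is read. Surveillance is added to the apparent device effect, and the part that can be compared fairly, events reported by subjects at visits held in both arms, is not shown on its own.

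**Working it through.** **Schedule, side by side**

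| Means of detection | Spatz3 | Control |
|---|---|---|
| Questioning about events at each visit through Week 32 (Sections 6.2.3, 4.3.4) | yes | yes |
| Protocol endoscopies for a typical subject | 3 (implantation, 18 weeks, extraction) | 0 |
| Further endoscopy (volume above 900 ml, unscheduled, ulcer follow-up) | provided for | not provided for |
| Blood count and chemistry panels after baseline | 1 | 0 |
| Planned follow-up | 56 weeks | 32 weeks |

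The visit table also marks event recording at implantation, adjustment and explantation, three occasions that controls do not have. The implantation endoscopy serves mainly to rule out contraindications, so for new lesions the typical number of scheduled looks is 2 against 0.

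**Would a cut at Week 32 be enough?** No. The 18-week endoscopy, and normally the extraction endoscopy, fall inside it. The cut does remove the Week 36 panel. It leaves the panel in for a subject extracted before Week 28, because the panel then falls before 28 + 4 = 32 weeks.

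**Denominators.** Section 7.3 gives no figure, so the arm sizes come from Section 7.2. The net difference is 10.34 − 3.3 − 4.5 = 2.54, with SD 6.6, one-sided 2.5%, 80% power and 2:1 allocation. Control n = (1 + 1/2) × (1.960 + 0.842)² × 6.6² / 2.54² = 79.5, rounded up to 80. With 160 Spatz3 subjects the total is 240, as stated, and power is 80.2%. Then 240 / 0.85 = 282.35, against the stated 282 (188 and 94). The efficacy sample size is not affected by this point.

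**Illustration of surveillance alone.** The documents give no rate of silent findings. Assume a proportion p in each arm has a silent finding during follow-up that the device did not cause, that a share s of these is detected in Spatz3 and none in control, and that all 188 and 94 are followed. Expected Spatz3 count = 188 × p × s. Recorded control count = 0. True control count = 94 × p.

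| p | Spatz3 recorded, s = 1 | Spatz3 recorded, s = 0.5 | Control recorded | Control true |
|---|---|---|---|---|
| 2% | 3.8 | 1.9 | 0 | 1.9 |
| 5% | 9.4 | 4.7 | 0 | 4.7 |
| 10% | 18.8 | 9.4 | 0 | 9.4 |
| 20% | 37.6 | 18.8 | 0 | 18.8 |

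No test is planned. As a yardstick for how such a row would look, 9 of 188 (4.8%) against 0 of 94 is the smallest split with a two-sided Fisher p below 0.05 (p = 0.032). With no true difference, the chance of 9 or more in Spatz3 is 1.4%, 60%, 99.7% and over 99.9% at p = 2%, 5%, 10% and 20% with s = 1. With s = 0.5 it is about 0.01%, 4.8%, 60% and 99.7%. The effect thus runs from negligible to dominant, depending on two quantities that the documents do not supply.

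**Follow-up length, a second difference.** With an equal constant hazard, a 32-week risk r becomes 1 − (1 − r)^(56/32) at 56 weeks. Risks of 5%, 10%, 20% and 40% become 8.6%, 16.8%, 32.3% and 59.1%. This applies to subjects who keep the balloon to Week 32. Those extracted earlier are followed for 24 weeks from extraction.

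**The case against.** The strongest reply is that nothing is decided on these rows. Section 7.3 summarizes, with no safety test and no between-arm safety hypothesis. Section 3.2.2 is about device-related events, and the ulcer stopping rule in Section 6.3.2 uses implanted subjects only. Events are also shown by causality, and the Data Monitoring Committee makes the final call on relatedness. The asymmetry raises the Spatz3 rate, so it cannot make the device look safer than it is. All of this stands, and it limits the point to reporting. It does not make the control column a background rate, and judging relatedness in Spatz3 cannot supply findings never sought in controls.

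The background of silent lesions may also be small. The exclusion criteria in both arms cover inflammatory gastrointestinal disease, positive H. pylori and daily gastric irritants. The implantation endoscopy additionally screens Spatz3 subjects for esophagitis, erosive gastritis and ulcer. Lesions seen later in Spatz3 are then largely new and arise with a balloon in place. This stands as a reason not to assume any particular size.

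The laboratory part is conditional. Section 6.2.2 leaves clinical significance to the investigator's judgement, so an abnormal value need not become an adverse event. Nor does the protocol text show what the diabetic follow-up form (CRF11) records in each arm.

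A reader might put a figure on the defect from the ulcer thresholds of 10% and 20% in Sections 6.1 and 6.3.2 (0.10 × 188 = 19 and 0.20 × 188 = 38 subjects), or from the 10.3% to 39.6% ulceration reported in Section 2.2 for another balloon. The documents do not support that. The first are monitoring limits and the second is a total ulcer rate for a different device. Neither is a silent or background rate.

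**Conclusion.** The point holds as a matter of how safety is tabulated. For ulcer, gastritis and esophagitis, and for scheduled-laboratory abnormalities that the investigator judges to be adverse events, the by-arm rows mix device effect with surveillance of one arm. The schedule alone establishes this: typically 3 protocol endoscopies against 0, and 1 post-baseline panel against 0.

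The size is unknown. The illustration rests on assumed prevalence and detection, equal in both arms for prevalence, and serves only to show that it could be trivial or large.

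Two stronger readings should be resisted. One is that the plan formally compares adverse event rates and that this comparison is biased; no such comparison is specified. The other is that events in controls cannot be found at all. Controls are questioned at every visit through Week 32, so events with symptoms are ascertained, and only findings that need an endoscope or a scheduled panel escape the protocol. The remedy is a cheap improvement. It repairs no decision rule.

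**What to change.** Amend Section 7.3 as follows:

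1. Keep the full by-arm summary of all adverse events and serious adverse events. Add a note that controls had no protocol endoscopy and no post-baseline laboratory panel.
2. Add a by-arm table through Week 32 limited to events ascertained alike in both arms: those reported spontaneously or elicited at visits, counted as the presenting symptom or clinical event.
3. Tabulate lesions found at any endoscopy, scheduled or unscheduled, and abnormalities from the Week 36 or four-weeks-post-extraction panel, for Spatz3 only, as rates among subjects examined, with no control column.
4. Show events after Week 32 separately.
5. Record mode of detection on the adverse event form (scheduled endoscopy, unscheduled endoscopy, laboratory panel, spontaneous or elicited report). CRF12 is listed among the appendices but its content is not available here, so this applies only if the field is not already there.

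Three details matter. Unscheduled endoscopy belongs in item 3 because it is provided for in one arm only; the symptom that prompted it still counts in item 2. Splitting lesions by whether symptoms came first would separate little, since Table 1 in Section 6.2.2 expects nausea, pain and heartburn in nearly all balloon patients. Mode of detection should not be derived from dates, because Sections 6.1 and 6.3.2 date an ulcer at its confirmatory endoscopy whether or not symptoms preceded it.

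The cost is one form field, some extra coding, and one or two tables. No event is dropped, no visit, endoscopy or laboratory test is added, and no stopping rule, clinical rule or efficacy analysis changes.
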